9.5. Follow-up of adverse events, serious adverse events, and pregnancies

9.5.1. Follow-up of adverse events and serious adverse events

9.5.1.1. Follow-up during the study

After the initial AE/SAE report, the investigator is required to proactively follow each subject and provide additional relevant information on the subject's condition to GSK Biologicals (within 24 hours for SAEs; refer to Table 21).

All SAEs and AESIs (serious or non-serious) documented at a previous visit/contact and designated as not recovered/not resolved or recovering/resolving will be reviewed at subsequent visits/contacts until the last visit of the subject.

All AEs documented at a previous visit/contact and designated as not recovered/not resolved or recovering/resolving will be reviewed at subsequent visits/contacts until 30 days after the last vaccination.

205626 (S SONNEI MONO GMMA SBVGH-003 [H03_03TP])
Protocol Amendment 6 Final

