Reiter's syndrome	A post-dysenteric reactive arthritis, with ocular and/or urethral inflammation, which has an onset typically 1 to 3 weeks after the onset of diarrhea, has been reported to occur in patients with shigellosis.	negative Shigella cultures in stools. Data suggest that the risk of reactive arthritis following shigellosis may be higher in persons carrying the human leukocyte antigen (HLA)-B27, thus the exclusion of subjects with a positive HLA-B27 test at screening.							

205626 (S SONNEI MONO GMMA SBVGH-003 [H03_03TP])
Protocol Amendment 6 Final

Important Potential/Identified Risk	Data/Rationale for Risk	Mitigation Strategy
Risk related to antibacterial therapy	Other (challenge phase) There are documented side effects with the use of antibiotics.	However, ciprofloxacin, the antibiotic given to all subjects on the 5th day after challenge, is generally well-tolerated. The most frequently reported drug related events for all indications of ciprofloxacin therapy have been nausea, diarrhea, abnormal liver function tests, vomiting, and rash which are all mild to moderate in most cases. The most common symptoms that happen after taking TMP-SMX are nausea, vomiting, loss of appetite, skin rash and itching. All subjects will be monitored closely and given adequate care when the need arises.

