3.2. Challenge Phase

Four weeks after completion of the two-dose vaccination schedule (approximately 28 days after Visit 3) subjects will be admitted the day before the challenge date (Day 56) and will stay for 9 days in the inpatient unit. Biological sample collection could start for logistical reason at Day 56 (the day of admission before challenge). The day of challenge (Visit 5; Day 57), they will be administered a 1500 CFU challenge dose of *S. sonnei* 53G. Before receiving the challenge, all inclusion and exclusion criteria and hematology will be assessed.

When assessing inclusion and exclusion criteria, the investigator will also inquire about antibiotic treatment during the week prior to the challenge date. Any subject who had a course of antibiotic the week prior to challenge, will not receive the challenge agent.

Subjects will fast for 90 minutes prior to receiving the *S. sonnei* 53G challenge inoculum and an additional 90 minutes after challenge. All subjects in the same cohort will be challenged in the same day using the same inoculum, which will ensure the consistency of the dose used. Approximately 5 minutes before drinking the challenge suspension, the subject will drink a 120 mL solution of sodium bicarbonate to neutralize gastric acidity. A subject with fever or signs of acute illness will not receive the challenge agent and any subject who vomits following ingestion of the challenge agent will not be re-dosed. A note will be made in the subject source documents regarding the apparent amount of the vomitus (small, moderate or large). The subject will still continue in the study and undergo all study-related procedures. Care will be taken to ensure that a minimum amount of time, not to exceed 2 hours, is spent between the reconstitution of the challenge inoculum and the oral administration of the inoculum to the subject.

Two mL of the inoculum will be retained for pre- and post-challenge quantification of the dose. Aliquots of the retained inoculum will be streaked onto trypticase soy agar (TSA) plates and after incubation, average number of colonies on the TSA plates will be counted and CFU/mL will be calculated. Study staff will take all necessary precaution needed for handling of *S. sonnei* 53G and adhere to the CCHMC policy and procedures.

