- They have diarrhea (any severity stool Grade 3 or higher) and two or more of the following symptoms: severe abdominal pain/cramps, severe nausea, severe headache, severe myalgia, severe arthralgia, gross blood in ≥ 2 stools, any fever (≥ 38.0°C measured orally), or any vomiting.
- They experience unexpectedly severe events such as hypotension (disproportionate to volume loss), renal dysfunction, or altered mental state (e.g. somnolence) at the discretion of the investigators.
- A study physician determines early treatment is warranted for other reasons.

A subject receiving early antibiotic treatment will still remain on the unit until the planned day of discharge (the 9th day of inpatient stay: Day 65). On that day, if a subject is clinically well and has had at least 2 negative stool cultures, collected at least 6 hours apart, for *S. sonnei*, s/he will be discharged. A subject that, on the planned day of discharge, still had S. *sonnei* isolated from the Day 64 stools will be asked to remain in the unit until s/he is no longer shedding. A subject still shedding 48 hours after initiation of ciprofloxacin will be switched to a Septra DS (1 tablet twice a day for five days). If a subject is still positive 48 hours after the second-line antibiotic is administered, a culture and antibiotic sensitivity test will be obtained and therapy initiated based on sensitivity results. If a subject has two consecutive negative stool samples and is eligible to be discharged from the inpatient stay but did not finish his treatment course, s/he can be given the remaining doses to complete at home.

Following discharge, subjects will return at 28 days (Visit 6), 56 days (Visit 7) and 6 months (Visit 8) after challenge for outpatient clinical assessment. During these visits, clinical assessment will be done to assess their general health status and find out about the occurrence of AESI, any AE and SAE.

[figure not shown]
Subjects will be advised at the time of their discharge to contact the study staff/doctor if they feel unwell. The subjects will be followed up until 6 months after the challenge. At the last study visit, at 6 months after challenge, the subject will be reviewed for the occurrence of any AESI and the site staff will ensure all AEs are resolved.

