- ⁴ Sampling to be done 7 days after challenge agent administration (i.e., Day 64).
- ⁵ Additionally, hematology is repeated weekly until resolution if neutropenia occurs. On the day of vaccination/challenge, sampling will be done before vaccination/challenge.
- ⁶ Urine dipstick to be done for all subjects and, in case of abnormal results, a urine culture is to be performed (urinalysis).
- ⁷ Before vaccination/challenge (Day 1/Day 57 sample can be collected by the subject at most a week before and stored as described in the Investigator Manual and SPM.
- ⁸ Sampling to be done daily during inpatient stay and if subject is still shedding 7 days post-challenge administration (Day 64). However, all subjects even if not shedding anymore will remain in the inpatient stay until 7 days post-challenge and will be discharged on Day 65.
- ⁹ Samples collection can be performed between Day 56 and Day 57.

205626 (S SONNEI MONO GMMA SBVGH-003 [H03_03TP]) Protocol Amendment 6 Final

Whenever possible, the investigator should arrange study visits within the interval described in Table 5.

Table 5 Intervals between study visits (Amended: 23 July 2019)

Interval	Optimal length of interval	Allowed interval
Screening visit → Visit 1	-7 days	-45 days – -1 days
Visit 1 → Phone Call	3 days	2 days - 6 days
Visit 1 → Visit 2	7 days	7 days - 10 days
Visit 1 → Visit 3	28 days	26 days - 33 days
Visit $3 \rightarrow$ Phone call	3 days	2 days - 6 days
Visit 3 → Visit 4	7 days	7 days - 10 days
Visit 3 → Visit 5	28 days	26 days - 33 days
Visit 5 → Inpatient stay	9 days	9 days - as needed
Visit 5 → Visit 5 post-challenge blood draw (Amended: 23 July 2019)	7 days (Amended: 23 July 2019)	7 days – 10 days (Amended: 23 July 2019)
Visit 5 → Visit 6	28 days	28 days - 35 days
Visit 5 → Visit 7	56 days	49 days - 63 days
Visit 5 → Visit 8	180 days	166 days - 194 days

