9.1.3.3. Solicited events after challenge phase

During the challenge phase after the subjects have received the challenge agent, events associated with the administration of the challenge agent will be collected and recorded by the investigator in the CRF. These events include diarrhea, abdominal pain, abdominal cramps, gas, anorexia, nausea, headache, myalgia, malaise, arthralgia, fever, and vomiting beginning the day of administration of study challenge agent until 7 days after challenge (i.e., Day 64). Any unresolved events will be followed to resolution or stabilization. Oral rehydration will be initiated and recorded for subjects with a Grade 2 or higher AE of diarrhea, vomiting, dysentery or dehydration. The hydration of subjects developing diarrhea will be maintained with oral electrolyte solutions by offering at least 1.5 mL for each gram of diarrheal stool lost, as tolerated. Subjects who develop vomiting will be offered at least 1.0 mL for each gram of emesis lost, as tolerated. Subjects will be evaluated by a physician who will consider intravenous hydration for subjects who:

- Cannot tolerate oral fluids,
- Experience fluids loss that exceeds their ability to drink replacement fluids,
- Have > 1000 mL deficit in intake in a 24 hour period,
- Experience weight loss of more than 5%,
- Have urine specific gravity > 1.030 for 12 hours,
- Have syncope or near-syncope,
- Grade 3 tachycardia, or
- Grade 3 hypotension.

If the subject is unable to tolerate fluids by mouth and intravenous fluids are deemed necessary by the assessing physician, a 0.9% sterile saline solution 1-liter bolus will be administered intravenously. This bolus will be repeated as needed to resolve Grade 2 and above symptoms at the discretion of assessing physician. Fluid maintenance will be continued using 0.45% NaCl, 5% dextrose, and 20 mEq KCL per liter at a rate of 100 mL/hour until subject is able to resume oral rehydration. If the subject develops grade 4 hypotension despite the aggressive fluid management, the subject will be transferred from the inpatient unit to a hospital setting.

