9.1.4. Unsolicited Adverse Events

An unsolicited AE is an AE that was not solicited using a Subject Diary and that was spontaneously communicated by a subject who has signed the informed consent or a solicited local or systemic AE that continues beyond the solicited period at day 7 after vaccination.

Potential unsolicited AEs may be medically attended (defined as symptoms or illnesses requiring hospitalization, or emergency room visit, or visit to/by a health care provider), or were of concern to the subjects. In case of such events, subjects will be instructed to contact the site as soon as possible to report the event(s). The detailed information about the reported unsolicited AEs will be collected by the qualified site personnel during the interview and will be documented in the subject's records.

205626 (S SONNEI MONO GMMA SBVGH-003 [H03_03TP]) Protocol Amendment 6 Final

Unsolicited AEs that are not medically attended nor perceived as a concern by subjects will be collected during interview with the subjects and by review of available medical records at the next visit

Unsolicited AEs will be collected until 28 days after each vaccination and until 28 days after challenge.

9.1.5. Clinical laboratory parameters and other abnormal assessments qualifying as adverse events or serious adverse events

In absence of diagnosis, abnormal laboratory findings (e.g., clinical chemistry, hematology, urinalysis) or other abnormal assessments that are judged by the investigator to be clinically significant will be recorded as AE or SAE if they meet the definition of an AE or SAE (refer to Sections 9.1.1 and 9.1.2). Clinically significant abnormal laboratory findings or other abnormal assessments that are present at baseline and significantly worsen following the start of the study will also be reported as AEs or SAEs.

The investigator will exercise his or her medical and scientific judgment in deciding whether an abnormal laboratory finding or other abnormal assessment is clinically significant. Clinically significant modifications in hematology will be assessed by medical judgment based on interpretation of deviations from institution's normal values and recommendations from CBER FDA GUIDANCE FOR INDUSTRY: Toxicity Grading Scale for Healthy Adults and Adolescent Volunteers Enrolled in Preventive Vaccine Clinical Trials and predefined list of sign and symptoms related to neutropenia.

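### Section 9.5.1.1 ends review of ordinary unresolved AEs about the day of challenge, in conflict with the protocol's own post-challenge collection period and 6-month follow-up

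*Protocol*

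**What the plan says.** Protocol Section 9.5.1.1 sets two review periods for events that have not resolved. The first covers "All SAEs and AESIs (serious or non-serious) documented at a previous visit/contact" and runs to the subject's last visit. The second covers all AEs, which "will be reviewed at subsequent visits/contacts until 30 days after the last vaccination". The second period makes no mention of the challenge.

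Four other places bear on the same events:

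- **Section 9.1.4:** "Unsolicited AEs will be collected until 28 days after each vaccination and until 28 days after challenge". Section 9.3.1 sets the same recording period.
- **Section 3.2:** the outpatient visits after discharge (Visits 6, 7 and 8) ask about any AE, and at the 6-month visit "the site staff will ensure all AEs are resolved".
- **Section 9.1.3.3**, on solicited events after challenge: "Any unresolved events will be followed to resolution or stabilization".
- **Section 9.5.1.2:** separate rules, applying after discharge from the study, for SAEs, AESIs, withdrawals caused by an AE, and non-serious neutropenia.

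**The concern.** The review limit is anchored to the second vaccination, but the event that will make most subjects ill is the challenge four weeks later. A limit of 30 days after vaccination therefore runs out almost as soon as the challenge phase begins. A site with an ordinary AE still open at discharge finds one section telling it that review ended on about Day 59 and another telling it to carry the event to the 6-month visit.

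Safety after challenge is a secondary objective, and unsolicited AEs within 28 days of challenge are a listed endpoint. Section 9.3.3.3 asks for an outcome for every unsolicited AE. If sites apply 9.5.1.1 as written, the last recorded outcome of such an event may simply be its status when review stopped. Outcome and duration would then be incomplete in both groups, and possibly uneven between subjects, depending on which section the staff followed.

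**Working it through.** **Inputs.** Visit 3, the last vaccination, is Day 29 (Tables 4 and 14). For the challenge, Section 3.2 states: "The day of challenge (Visit 5; Day 57), they will be administered". Table 5 gives the visit intervals: Visit 3 to Visit 5, 28 days (allowed 26 to 33); Visit 5 to Visit 6, 28 days (allowed 28 to 35); Visit 5 to Visit 7, 56 days; Visit 5 to Visit 8, 180 days. The windows are advisory: "Whenever possible, the investigator should arrange study visits within the interval described in Table 5".

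**The protocol's own calendar, reproduced.**
- Challenge: 29 + 28 = Day 57.
- End of unsolicited AE collection, and Visit 6: 57 + 28 = Day 85.
- Visit 7: 57 + 56 = Day 113.
- Visit 8: 57 + 180 = Day 237.

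All agree with Table 4.

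**The limit in 9.5.1.1.** 29 + 30 = Day 59. That is 59 − 57 = 2 days after challenge and 85 − 59 = 26 days before AE collection ends.

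**Effect of the visit window.** Let g be the number of days from Visit 3 to Visit 5. Measured from challenge, the limit falls at 30 − g days.

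| g (days) | Limit relative to challenge |
|---|---|
| 26 | 4 days after |
| 28 | 2 days after |
| 30 | same day |
| 33 | 3 days before |

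The window from Visit 1 to Visit 3 does not matter here, because Table 5 times the challenge from Visit 3 and both dates move together.

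**Which visits remain inside the limit.** Within the windows, the limit is at most 4 days after challenge and Visit 6 is at least 28 days after it. The shortfall is therefore at least 28 − 4 = 24 days. No subject seen within the windows has an outpatient post-challenge visit before the limit.

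**Which rule governs which event after challenge.**
- SAEs and AESIs: 9.5.1.1, to the last visit. No conflict.
- Neutropenia cases and AEs leading to withdrawal: own rules in 9.5.1.2.
- Solicited challenge events, collected to Day 64: 9.1.3.3 follows them until they resolve or stabilise, while 9.5.1.1, which speaks of all AEs, stops at about Day 59. Conflict.
- Other unsolicited AEs: 3.2 carries them to Visit 8, while 9.5.1.1 stops at about Day 59. Conflict.

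**An illustration.** Section 1.3.1 lists reactive arthritis among the challenge risks, "which has an onset typically 1 to 3 weeks after the onset of diarrhea". Diarrhea caused by the challenge cannot start before the challenge, so a typical onset is at least 7 days after it, nominally 57 + 7 = Day 64 or later. The limit is never more than 4 days after challenge, so it has always passed. The only AESI in Table 17 is symptomatic neutropenia, so a non-serious arthritis would fall under the expired limit.

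**The case against.** The strongest reply is that the protocol does have a follow-up rule for these events. Section 3.2 asks about AEs at Visits 6 to 8 and expects all of them to be resolved by the last visit. Table 4 schedules a history-directed examination at each of those visits, and 9.5.1.1 itself opens with a general duty to follow each subject actively. A reader might infer from 9.5.1.1 that post-challenge AEs have no follow-up rule at all. The documents do not support that: two rules exist and disagree.

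Other parts of the reply also stand:

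- **Detection is not shortened.** The limit concerns AEs already documented. The 26 days between Day 59 and Day 85 are not days of lost AE collection; an arthritis starting in that period would still be recorded. Its likelihood is also reduced by excluding HLA-B27 positive subjects.
- **Section 9.1.3.3 covers solicited events only.** It contradicts the all-AE wording of 9.5.1.1, but it is no rule for unsolicited AEs. For those, the conflict is with 3.2 and with the collection period.
- **An unresolved outcome is a permitted category** in 9.3.3.3, and nothing in 9.5.1.1 forbids later review.

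One might also count the challenge as the last vaccination. The protocol does not use the word that way; Section 9.1.4 names vaccination and challenge separately in one sentence. Even on that reading the limit would be 57 + 30 = Day 87, before Visits 7 and 8 (Days 113 and 237), and the conflict with 3.2 would remain.

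**Conclusion.** The point holds as an internal contradiction in a conduct rule. For ordinary AEs, 9.5.1.1 ends review nominally on Day 59, between 4 days after and 3 days before challenge under the allowed Visit 3 to Visit 5 interval. Section 3.2 carries the same events to the 6-month visit. This rests on the nominal calendar, on the Table 5 windows being kept, and on the literal meaning of vaccination.

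The consequence is limited to outcome and duration data for AEs outside the exempt groups, mainly unsolicited AEs open after challenge. The primary efficacy endpoint and the count of AEs are untouched. How many events would be left without a final outcome cannot be estimated from the protocol, so a claim that this would happen often is not supported. The matter should be corrected, but it does not threaten the trial's main conclusion.

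**What to change.** In Section 9.5.1.1, replace the limit of 30 days after the last vaccination with the subject's last visit (Visit 8), as that section already does for SAEs and AESIs. Reconcile the wording with Sections 3.2 and 9.1.3.3, so that all three name the same end of review and say whether a stabilised event counts as closed; at present 3.2 speaks only of resolution. An AE still open at Visit 8 can then be recorded with its status under Section 9.3.3.3.

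The cost is one sentence in an amendment, plus a check of open AEs at Visits 6, 7 and 8. These visits are already scheduled and already include a clinical assessment. No visit, sample or analysis is added.

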9.5.1.2. Follow-up after the subject is discharged from the study

The investigator will follow subjects:

- With SAEs, AESIs (serious or non-serious), or subjects withdrawn from the study as a result of an AE, until the event has resolved, subsided, stabilized, disappeared, or until the event is otherwise explained, or the subject is lost to follow-up.
- With other non-serious neutropenia cases, until the event is otherwise explained or they are lost to follow-up.

If the investigator receives additional relevant information on a previously reported SAE, he/she will provide this information to GSK Biologicals using a paper/electronic Expedited Adverse Events Report and/or pregnancy report as applicable.

GSK Biologicals may request that the investigator performs or arranges the conduct of additional clinical examinations/tests and/or evaluations to elucidate as fully as possible the nature and/or causality of the AE or SAE. The investigator is obliged to assist. If a subject dies during participation in the study or during a recognized follow-up period, GSK Biologicals will be provided with any available post-mortem findings, including histopathology.

9.5.2. Follow-up of pregnancies

Pregnant subjects will be followed to determine the outcome of the pregnancy. At the end of the pregnancy, whether full-term or premature, information on the status of the mother and child will be forwarded to GSK Biologicals using the electronic pregnancy report and the Expedited Adverse Events Report if applicable. Generally, the follow-up period doesn't need to be longer than six to eight weeks after the estimated date of delivery.

Regardless of the reporting period for SAEs for this study, if the pregnancy outcome is a SAE, it should always be reported as SAE.

9.6. Treatment of adverse events

Treatment of any AE is at the sole discretion of the investigator and according to current good medical practice. Any medication administered for the treatment of a SAE/AESIs should be recorded in Expedited Adverse Event Report of the subject's eCRF (refer to Section 7.6).

9.7. Unblinding

GSK Biologicals' policy (which incorporates ICH E2A guidance, EU Clinical Trial Directive and US Federal Regulations) is to unblind the report of any SAE which is unexpected and attributable/suspected to be attributable to the study vaccine/placebo or challenge agent, prior to regulatory reporting. The GSK Biologicals' Central Safety Physician is responsible for unblinding the treatment assignment in accordance with the specified timeframes for expedited reporting of SAEs (refer to Section 9.4.1).

205626 (S SONNEI MONO GMMA SBVGH-003 [H03_03TP])
Protocol Amendment 6 Final

9.8. Emergency unblinding

Unblinding of a subject's individual treatment code should occur only in the case of a medical emergency, or in the event of a serious medical condition, when knowledge of the treatment is essential for the clinical management or welfare of the subject, as judged by the investigator.

The emergency unblinding process consists of an automated system SBIR that allows the investigator to have unrestricted, immediate and direct access to the subject's individual study treatment.

The investigator has the option of contacting a GSK Biologicals' On-call Central Safety Physician (or Backup) if he/she needs medical advice or needs the support of GSK to perform the unblinding (i.e. he/she cannot access the automated Internet-based system).

Any emergency unblinding must be fully documented by using the Emergency Unblinding Documentation Form, which must be appropriately completed by the investigator and sent within 24 hours to GSK Biologicals.

GSK Biologicals' Contact information for Emergency Unblinding 24/24 hour and 7/7 day availability
GSK Biologicals' Central Safety Physician:
For US/Canada only: (GSK Biologicals Central Safety Physician on-call)
GSK Biologicals' Central Safety Physician Back-up:
US/Canada only:
Emergency Unblinding Documentation Form transmission:
US/Canada only: Fax: PPD

